1. SYNOPSIS

Title	Evaluating the Long- Term Immunogenicity of AD / MVA Ebola Virus Vaccines following late boosting with AD26.ZEBOV vaccine administered after heterologous prime/boost schedules of adenoviral and MVA vectored Ebola vaccines in healthy Senegalese adult volunteers aged 18-50 years: an open-label clinical trial
Short Title	Re -evaluating in Senegal Optimal Vaccine Schedules against E bola (RESOLVE)
Trial Centre(s)	Institut de Recherche en Santé, de Surveillance Epidemiologique et de Formation (IRESSEF), Dakar, Senegal
Funders	Innovate UK
Sponsor	University of Oxford
Trial Identifier	RESOLVE
Clinical Phase	II
Active Ingredients of Vaccines	AD26.ZEBOV – This is a viral vectored vaccine using an adenovirus as a vector expressing the Mayinga variant glycoprotein of the Ebola virus.
Design	Open- label clinical trial design
Population	Healthy adult volunteers aged 18 – 50 years from previous EBL 06 clinical trial led by IRESSEF and University of Oxford (UOXF) Investigators
Planned Trial Period	Study visits: April 2019 to December 2020
Sample Size	Up to 40 (50% recruitment anticipated, approximately 20)
Finished Products	AD26.ZEBOV at a dose of 5 x 10 ¹⁰ vp
Form	Liquid
Route of Administration	Intramuscular needle injection into the deltoid region of the non-dominant arm
Follow-up Duration	1 year from the date of the booster dose (52 weeks)
Primary Objective	To assess humoral and cellular immunity against Ebola virus glycoprotein at 1 year following a late booster dose of AD26.ZEBOV administered 3 to 4 years after receiving heterologous prime/boost of ChAd3- EBO Z /MVA –EBO Z administered at a 7 day interval
Secondary Objectives	Safety Safety and reactogenicity of late booster dose of AD26.ZEBOV administered 3 to 4 years after heterologous prime/boost schedules of adenoviral and MVA vectored Ebola vaccines
	Immunogenicity
	Humoral and cellular immunity against Ebola virus glycoprotein at 1 month following a late

	booster dose of AD26.ZEBOV administered 3 to 4 years after heterologous prime/boost schedules of adenoviral and MVA vectored Ebola vaccines
Safety Evaluation	Local and systemic solicited and unsolicited adverse events will be assessed. Safety blood tests will be obtained on Days 0, 7 and 28.
	Solicited adverse events will be recorded daily for 7 days post-vaccination
	Unsolicited AEs of all severities will be recorded from receipt of vaccination through 28 days post-vaccination.
	After study Day 28, only SAEs or new chronic medical conditions that require ongoing medical management will be recorded through to the last study visit.
Immunogenicity Evaluation	 Immunogenicity will be assessed by a variety of immunological assays and will include: Humoral- Ebola GP specific IgG as measured by ELISA
	 Cellular- Ebola GP specific T cell cytokine response measured using ex vivo interferon-γ enzyme-linked immunosorbent spot (ELISPOT)
	Exploratory outcome measures will include Ebola GP specific T cell cytokine response measured using intracellular staining technique, multicolour flow cytometry and neutralisation assays for antibodies
	Bleeding time points for immunological assays will be: Day 0, 7, 28 and 365
Statistical Analysis	Descriptive

2. ABBREVIATIONS

•	AE	Adverse event
•	aPTT	Activated Partial Thromboplastin Time
•	ChAd3 EBO Z	Chimapnzee Adenovirus 3 encoding the Ebola Zaire glycoprotein
•	CBF	Clinical Bio-manufacturing Facility
•	CCVTM	Centre for Clinical Vaccinology and Tropical Medicine
•	CI	Confidence Interval
•	CRF	Case Report Form
•	DSMB	Data Safety Monitoring Board
•	DSUR	Development Safety Update Report
•	ELISA	Enzyme-linked immunosorbant assay
•	ELISPOT	Enzyme-Linked Immunospot
•	GCP	Good Clinical Practice
•	GMO	Genetically Modified Organisms
•	GP	Glycoprotein
•	GSK	GlaxoSmithKline
•	HBsAg	Hepatitis B surface Antigen
•	HBV	Hepatitis B virus
•	HCG	Human Chorionic Gonadotrophin
•	HCV	Hepatitis C virus
•	HIV	Human Immunodeficiency Virus
•	HLA	Human Leucocyte Antigen
•	IB	Investigator Brochure
•	ICH	International Conference on Harmonisation
•	ICS	Intracellular Cytokine Staining
•	IFNγ	Interferon gamma
•	IM	Intramuscular
•	IMP	Investigational Medicinal Product
•	IMPD	Investigational Medicinal Product Dossier
•	ISR	Internal Safety Review
•		Interuterine Device
•		
•		Local Safety Moniton
•	мнра	Medicines and Healthcare Regulatory Authority
•	Μνα	Modified vaccinia virus Ankara
•	NIH	National Institute of Health
•	OVG	Oxford Vaccine Group
•	PBMC	Peripheral Blood Mononuclear Cell
•	PCR	Polymerase Chain Reaction
•	PI	Principal Investigator
•	pfu	Plaque forming unit
•	PIS	Partcipant Information Sheet
•	РТ	Prothrombin Time
•	QA	Quality Assurance
•	QP	Qualified Person
•	SAE	Serious Adverse Event
•	SmPc	Summary of Product characteristics
•	SOP	Standard Operating Procedure
•	SUSAR	Suspected Unexpected Serious Adverse Reaction
•	vp	Viral particle
•	VRC	Vaccine Reasearch Centre, NIH
•	WHO	World Health Organisation

3. BACKGROUND AND RATIONALE

3.1 Background

Ebolavirus is one of three genera in the family Filoviridae, which along with Marburgvirus and Cuevavirus, are known to induce viral haemorrhagic fever. There are five distinct species in the genus Ebolavirus including Bundibugyo (BDBV), Reston (RESTV), Sudan (SUDV), Taï Forest (TAFV), and Zaire (EBOV).(1) ZEBOV and SUDV are the most pathogenic and have been associated with the major EVD outbreaks.(2) The Ebola virus is a large, negative-strand RNA virus composed of 7 genes encoding viral proteins, including a single glycoprotein (GP). (3-5)

Ebola virus causes outbreaks through person-to-person transmission. Infection results from direct contact with blood, secretions, organs or other bodily fluids of infected people, and indirect contact with environments contaminated by such fluids (2). People remain infectious with EVD as long as their blood and secretions contain the virus; the virus was isolated from semen 61 days after onset of illness in a man who was infected in a laboratory.(2) The high infectivity of blood and secretions puts healthcare workers at particularly high risk during outbreaks, and direct contact with the bodies of deceased victims also has a role in the transmission of the virus.

The incubation period of EVD is 2 to 21 days (7 days on average, depending on the strain) followed by a severe acute viral illness often characterised by the rapid onset of non-specific symptoms such as fever, extreme fatigue, pharyngitis, gastrointestinal complaints, abdominal pain, anorexia, headache, myalgia and/or arthralgia. These initial symptoms last for about 2 to 7 days after which more severe symptoms related to haemorrhagic fever occur, including haemorrhagic rash, epistaxis, mucosal bleeding, hematuria, hemoptysis, hematemesis, melena, conjunctival haemorrhage, tachypnoea, confusion, somnolence, and hearing loss. Laboratory findings include leucopenia, thrombocytopenia and elevated liver enzymes. (2) As the early symptoms are non-specific, diagnosis is difficult and it may take up to three days after symptoms start for the virus to reach detectable levels. Laboratory diagnostic tests such as PCR, ELISA testing and virus isolation can be carried out. In general, the symptoms last for about 7 to 14 days after which recovery may occur. Death can occur 6 to 16 days after the onset of symptoms, and mortality rate has been reported in some outbreaks to be as high as 90% (2, 6, 7).

A primary antibody response (IgM) can be detected in the blood of infected persons 2 to 9 days after infection whereas IgG antibodies appear approximately 17 to 25 days after infection. This IgG response coincides with the recovery phase. In survivors of EVD, both humoral and cellular immunity are detected, however, their relative contribution to protection is unknown (8).

3.1.1 The need for an Ebola vaccine

EVD has occurred in numerous sporadic outbreaks since it was discovered in 1976. The recent EVD outbreak in West Africa in 2014, was the largest in history and recorded a total of 28,616 confirmed, probable, and suspected EVD cases, including 11,310 deaths in Guinea, Liberia, and Sierra Leone, between January 2014 and January 2016.(9) This outbreak was caused by the ZEBOV species of the virus. The recent Ebola virus outbreaks have been characterised by a high mortality rate ranging from 50% to 90%. Treatment options are limited and no specific antiviral drugs or preventative vaccines are currently licensed for use.

Almost all human cases of EVD are due to emergence or re-emergence of the Zaire and Sudan subtype of the virus. The persistence of the virus, evident from various serological surveys, makes this a serious global public health concern in an interconnected word. Emergence of the Reston subtype in animals poses a potential health risk in parts of Asia such as Philippines.

Future Ebola vaccines will be required to fulfil different needs (10). A vaccine to protect the frontline staff involved in providing care in future outbreaks will need to deliver highly effective and lasting protection (11). Countries with risk of future outbreaks can maintain a pool of vaccinated staff with sustained immunity which can be checked periodically. Such vaccines should prevent infection and virus shedding thereby interrupting onward transmission of the virus during an outbreak.

Vaccines for use during an outbreak in an EVD endemic zone will need to provide rapid protection from a single dose preferably, but would not need to provide long-lasting protection. The main purpose of such a vaccine would be to

reduce disease severity and death, as well as prevention of virus shedding to stop onward transmission. An assessment of sustained immunogenicity of a potential Ebola vaccine will, therefore, be necessary to determine its clinical utility.

Effective control of future Ebola virus outbreaks will require immediate availability of a sufficient cohort of healthcare workers and other frontline staff who are immunized to the infection and will not be a source of viral transmission. The duration of a persistent immunological response from a vaccine will determine whether additional booster dosage will be required to maintain a protective level of immunity in such a cohort. The sustainability of an immune response will also indicate how many such boosters will be required and at what intervals. All such information will be crucial in determining the Ebola vaccination policy by WHO and countries in the Ebola endemic zone.

3.2 Development of Ebola Vaccines

Ebola virus is a filovirus wih a 19-kb, non-segmented, negative-strand RNA genome that encodes 7 viral proteins.(12) The surface glycoprotein mediates viral entry into host cells.(8) This has been the primary antigenic target for vaccine development.(13) 3 early generation Ebola vaccine candidates were evaluated in clinical trials between 2003 and 2009.(14-16) There were no safety concerns but immunogenicity and preclinical efficacy data was deemed inadequate. (16)

The Vaccine Research Center (VRC), National Institute of Allergy and Infectious Diseases (NIAID), National Institutes of Health (NIH) developed a recombinant chimpanzee adenovirus Type 3-vectored Ebolavirus vaccine (cAd3-EBO), VRC-EBOADC069-00-VP. The vaccine encodes wild type (WT) GP from Zaire [GP (Z)] and Sudan [GP (S)] species of Ebola virus. The rationale for the development of this vaccine was based on pre-clinical studies (see Investigator Brochure), previous human experience with other investigational Filovirus vaccines and previous human experience with adenovirus vaccines and the cAd3 vaccine vector.(17) This single vaccination was shown to be safe and immunogenic. (18)

A vaccination strategy to achieve protective immunity in most recipients with a single vaccination would be desirable in an outbreak setting. Vaccination strategies that achieve durable protective immunity would be desirable for populations in areas of the world where outbreaks occur sporadically. Optimally, one approach would serve both needs, but a different approach may be needed for rapid immunity than is needed for durable immunity. The Phase 2 studies and efficacy trials are in progress.

In 2017, the results from a Phase 3 efficacy trial in Guinea testing the rVSV-vectored vaccine for preventing Ebola were published. This was a viral-vectored candidate expressing a surface glycoprotein of the Zaira strain. It was an open-label, cluster-randomised ring vaccination trial. The results suggested substantial protection against the Ebola virus, with no cases among vaccinated individuals in both randomised and non-randomised clusters from day 10 after vaccination. The results gathered from this trial suggest that such a vaccination may be effective in contributing to controlling an Ebola virus disease outbreak and that ring vaccination may also be highly effective.(19)

This trial differs from the previous EBL06 study in that the adenovirus we will be using is AD26. This is because ChAd3 is no longer manufactured by GSK. A previous Phase I study conducted in Oxford showed that AD26 ZEBOV is safe and well tolerated, with a similar reactogenicity profile to ChAd3 EBO Z, and induced comparable immune responses in schedules using an MVA vectored booster dose of vaccine.(20, 21)

3.2.1 AD26.ZEBOV

Pre-Clinical studies

A study to evaluate immunogenicity and protective efficacy of heterologous prime-boost regimens involving AD26, AD35 and MVA-BN-Filo vectors expressing different Ebola and Marburg proteins study in NHPs (Cynomolgus macaques) was performed in a small number of animals (2 per vaccine regimen). Full protection from Ebola virus disease after wild-type Ebola Kikwit 1995 challenge was observed in all recipients of heterologous regimens, with survivors showing only minor to no symptoms. All heterologous prime-boost regimens induced comparable immune responses against the EBOV Mayinga GP. Independently of the vaccine regimen, a strong boost effect was observed after heterologous prime-boost immunisation. As part of this study, safety assessments (non-GLP) were performed. Preliminary findings indicate that the NHPs appear to tolerate the vaccines, without signs of adverse effects. Two additional studies were performed involving more animals, to strengthen the robustness of the nonclinical efficacy data, and also to assess shorter schedules to be evaluated in the clinical program. Overall, the best protection against lethal outcome and Ebola virus disease was obtained with an 8 week prime/boost interval and AD26 as prime immunisation.

Toxicity testing in rabbits addressed general toxicity and reproductive toxicity of different heterologous prime-boost regimens using AD26.ZEBOV and MVA-BN-Filo, and a homologous prime-boost regimen using AD26.ZEBOV.

In a GLP-compliant, repeated dose toxicity study in rabbits, the different dose regimens were well tolerated when administered by IM injection with a 14-day interval period. All vaccine regimens elicited detectable EBOV GP-specific antibody titres. The immune response was associated with local test-article-related inflammatory changes at the injection sites, transient disturbances in blood and serum inflammatory parameters and microscopic findings of increased lymphoid cellularity in the draining iliac lymph nodes and spleen. The findings were noted to be recovering over a 2-week treatment-free period and were considered to reflect a non-adverse physiological response associated with vaccination. There were no effects noted that were considered to be adverse.

4. OBJECTIVES AND ENDPOINTS

4.1 Primary Objective

To assess humoral and cellular immunity against Ebola virus glycoprotein at 1 year following a late booster dose of AD26.ZEBOV administered 3 to 4 years after receiving heterologous prime/boost of ChAd3- EBO Z /MVA –EBO Z administered at a 7 day interval

4.2 Primary Outcome Measures

- Ebola GP specific IgG as measured by ELISA
- Ebola GP specific T cell cytokine response measured using ex vivo interferon-y enzyme-linked immunosorbent spot (ELISPOT)

4.3 Secondary Objectives

Safety

Safety and reactogenicity of late booster dose of AD26.ZEBOV administered 3 to 4 years after heterologous prime/boost schedules of adenoviral and MVA vectored Ebola vaccines

Immunogenecity

Humoral and cellular immunity against Ebola virus glycoprotein at 1 month following a late booster dose of AD26.ZEBOV administered 3 to 4 years after heterologous prime/boost schedules of adenoviral and MVA vectored Ebola vaccines

4.4 Secondary Outcome Measures

Safety

The specific endpoints for safety and reactogenicity will be actively and passively collected data on adverse events. The following parameters will be assessed for both groups:

- Occurrence of solicited local reactogenicity signs and symptoms for 7 days following the vaccination
- Occurrence of solicited systemic reactogenicity signs and symptoms for 7 days following the vaccination
- Occurrence of unsolicited adverse events for 28 days following the vaccination
- Change from baseline for safety laboratory measures
- Occurrence of serious adverse events during the whole study duration

Immunogenicity

- Humoral- Ebola GP specific IgG as measured by ELISA
- Cellular- Ebola GP specific T cell cytokine response measured using ex vivo interferon-γ enzyme-linked immunosorbent spot (ELISPOT)

Ebolavirus specific immunogenicity will be assessed by a variety of immunological assays. The primary immunogenicity outcome measures are ELISA IFN-gamma ELISPOT for T cell responses.

Exploratory outcome measures will include Ebola GP specific T cell cytokine response measured using intracellular staining technique (ICS) and multicolour flow cytometry performed with research samples collected at different study timepoints as well as other immunogenicity assays throughout the study. Antibody function will also be assessed using assays to measure neutralisation ability of antibodies to the Ebola glycoprotein. An evaluation of genetic factors associated with immune responses may also be undertaken. These may include:

- Assays to assess immunological aging, dysregulation and senescence, such as telomere length or expression of
 relevant markers and transcription factors.
- Assays to assess presence or absence of other factors affecting vaccine immunogenicity, such as antibodies against viral pathogens including cytomegalovirus.
- Determination of HLA-type

Both primary and exploratory immunology may involve collaboration with other specialist laboratories, including laboratories outside of Senegal (e.g. Europe and USA). This would involve transfer of serum/plasma and/or peripheral blood mononuclear cells (PBMC), but samples would be anonymised. Volunteers will be consented for this during the process of obtaining informed consent for the study.

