5.3 Administration of vaccines

Preparation should be done in a temperature controlled preparation unit on a clean table with limited access using aseptic technique.

All vaccines will be administered intramuscularly according to IRESSEF CT site standard SOP. For all groups, the vaccine will be administered intramuscularly into the deltoid muscle of either arm. Participants who consent to receiving a vaccine will receive a 0.5 ml dose of AD26.ZEBOV, containing 5 x 10^{10} vp. The vaccinating Investigator will wear gloves and eye protection. During administration of the vaccines, Advanced Life Support drugs, resuscitation equipment and trained personnel will be immediately available for the management of anaphylaxis. On vaccination day, vaccines will be allowed to thaw to room temperature and administered within 4 hours from the start of thawing.

On the vaccination day, before the injection, study participants will undergo clinical evaluation and samples will be collected for laboratory tests as per schedule of evaluations (Table 3). Pregnancy test results for women of reproductive age must be obtained prior to the study injection on Day 0. A volunteer who arrives at the clinic with fever (axillary temperature \geq 37.5°C) or evidence of an acute illness, which precludes administration of the vaccine, may be rescheduled to enroll on a different date. This is outlined in further detail in Section 6.4.4.

Injections will be administered IM by needle and syringe. When choosing an arm for the injection, the investigator should consider whether there is an arm injury or a local skin problem that precludes administering the injection or will interfere with evaluating the arm after injection. The vaccine will be administered by a senior member of the clinical trial team who is experienced in administering similar vaccines. There will also be another study personnel who will confirm that the right doses of the vaccine are given to the volunteers in each group. The volume, date and time of administration will also be documented in a vaccine dispensing log that will be regularly monitored by the PI and an External Monitor.

In keeping with good medical practice, acute medical care will be provided to volunteers for any immediate allergic reactions or other injury resulting from participation in this research study. Procedures for follow-up in the clinic after vaccination are described in detail in section 7 and Table 3.

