6.4.4 Exclusion criteria at the time of vaccination

The following conditions constitute contraindications to administration of vaccine at the time of vaccination; if any one of these occurs at the time scheduled for vaccination, the participant may be vaccinated at a later date, or withdrawn at the discretion of the Investigator:

- Acute disease at the time of vaccination defined as the presence of a moderate or severe illness with or without fever.
- Temperature of \geq 37.5°C at the time of vaccination.
- Positive pregnancy test on the day of vaccination.

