7.5.2 Vaccinations

Before the vaccination, the on-going eligibility of the volunteer will be reviewed. The vaccine will be administered as described above in sections 5. The injection site will be covered with a sterile dressing and the volunteer will stay in the IRESSEF Site for observation, in case of immediate adverse events. Observations will be taken 30 minutes after vaccination (+/- 5 minutes) and the sterile dressing removed and injection site inspected. The sterile dressing will be discarded according to local SOPs at IRESSEF.

Local solicited AEs	Systemic solicited AEs
Pain	Fever
Redness	Feverishness/Chills
Warmth	Joint pains
Swelling	Muscle pains
ltch	Fatigue
	Headache
	Nausea/vomiting
	Malaise

Diary cards will collect information on the timing and severity of the following solicited AEs:

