7.6 Trial Site

Screening, vaccinations and follow-up visits will take place at IRESSEF, Dakar, Senegal.

Table 1: Schedule of attendances for all participants.

Attendance study clinic	1*	2	-	3	4	5
Timeline (days)	-14	0	1-6	7	28	365
Window period (days)				-1/+3	-1/+3	±14
Informed Consent	Х					
Inclusion/Exclusion criteria	Х					
Physical exam [^]	х	х		х		
Medical history	Х	Х		Х		
Urinalysis	Х					
BHCG – Urine test [%]		Х				
Review contraindications	Х	Х				
Study Vaccination		Х				

AEs reviewed		Х~	Х	Х	Х	
SAEs reviewed		Х~	Х	Х	Х	Х
Daily home visits			Х			
HIV, HBV	2					
Haematology	2			2		
Biochemistry*	4			4		
Exploratory Immunology ^{\$}		30		30	30	30
Daily Volume (mL)	8	30		36	30	30
Max. Cumulative Volume (mL)	8	38		74	104	134

* = Screening visit; ^ = Physical observations include pulse, blood pressure, temperature; % = females only; * = Biochemistry will include Creatinine and ALT; ~ = 30 mins after vaccination. In the event of any abnormality with these or haematology tests, repeat tests will be performed. \$ = Exploratory Immunology will include ELISA, IFN-γ T cell ELISPOT and ICS. These will be outlined in detail in the separate immunomonitoring plan.

8. Assessment of Safety

Safety will be assessed by the frequency, incidence and nature of adverse events and serious adverse events arising during the study.

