8.6 Causality Assessment

For every unsolicited AE, an assessment of the relationship of the event to the administration of the vaccine will be undertaken. An intervention-related AE refers to an AE for which there is a probable or definite relationship to administration of a vaccine. An interpretation of the causal relationship of the intervention to the AE in question will be made, based on the type of event; the relationship of the event to the time of vaccine administration; and the known biology of the vaccine therapy (Table 2).

Table 2: Guidelines for assessing the relationship of vaccine administration to an AE.

No Relationship	No temporal relationship to study product and Alternate aetiology (clinical state, environmental or other interventions); and Does not follow known pattern of response to study product
Possible	Reasonable temporal relationship to study product; or Event not readily produced by clinical state, environmental or other interventions; or Similar pattern of response to that seen with other vaccines
Probable	Reasonable temporal relationship to study product; and Event not readily produced by clinical state, environment, or other interventions or Known pattern of response seen with other vaccines
Definite	Reasonable temporal relationship to study product; and Event not readily produced by clinical state, environment, or other interventions; and Known pattern of response seen with other vaccines

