9.2 Safety analysis

Safety analysis will be carried out for all vaccinated participants, regardless of whether or not they complete the study.

- Occurrence of each solicited adverse event within 7-day follow-up period (day of vaccination and 6 subsequent days) after vaccination
- Occurrence of unsolicited adverse events within 28 days (day of vaccination and 27 subsequent days) after vaccination
- Occurrence of serious adverse events within 28 days (day of vaccination and 27 subsequent days) after vaccination and over the whole study duration
- Occurrence of a serious adverse event from vaccination to the end of the study

Solicited and unsolicited AE data will be collected at each clinic visit. It will be collected by home visits, clinical review, clinical examination (including observations) and laboratory results. (See Table 3-5).

Hematological (hemoglobin, WBC and platelets) and biochemical (creatinine and ALT) laboratory values will be presented according to toxicity grading scales and tabulated by group.

SAEs, AEs of special interest and withdrawal due to AE(s)/SAE(s) will be described in detail.

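### Mild systemic symptoms already present before the injection can be counted as reactogenicity, because no graded pre-dose record and no new-or-worsened rule is specified

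*Protocol*

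**What the plan says.** Section 4.4 lists among the secondary safety outcomes: "Occurrence of solicited systemic reactogenicity signs and symptoms for 7 days following the vaccination". Section 9.2 gives the counting rule: "Occurrence of each solicited adverse event within 7-day follow-up period (day of vaccination and 6 subsequent days) after vaccination". Neither asks that the symptom be new or worse than before the dose.

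The systemic list in Section 7.5.2 is fever, feverishness/chills, joint pains, muscle pains, fatigue, headache, nausea/vomiting and malaise. On the symptom scale in Section 8.8 (captioned Table 4), being aware of a tolerable symptom is enough for Grade 1. The same section of the protocol introduces the diary: "Diary cards will collect information on the timing and severity of the following solicited AEs" (Section 7.5.2).

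Before the injection, Section 5.3 says that "before the injection, study participants will undergo clinical evaluation and samples will be collected for laboratory tests". Table 1 (Section 7.6) schedules a physical examination, medical history and review of contraindications on Day 0. Its Day 0 adverse event review carries the footnote "30 mins after vaccination".

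Among the Section 6.4.4 grounds for deferral or withdrawal at vaccination is "Acute disease at the time of vaccination defined as the presence of a moderate or severe illness with or without fever"; raised temperature is another. Section 8.6 provides a causality step: "For every unsolicited AE, an assessment of the relationship of the event to the administration of the vaccine will be undertaken". It mentions no such step for solicited events.

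**The concern.** Apart from measured fever, the systemic items are subjective and common in everyday life, and the threshold for Grade 1 is low. The deferral rule addresses moderate or severe illness, so a volunteer with a mild symptom can be vaccinated. If that symptom is still there at the 30-minute review or on the first diary day, nothing in the protocol tells staff how to treat it, and no causality step follows that could set it aside.

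Every participant receives AD26.ZEBOV. The references to both groups in Section 4.4 and to booster groups in Section 9.3 do not create an unvaccinated arm, so background symptoms cannot be netted out by comparison.

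Safety and reactogenicity of the late booster are a stated secondary objective (Section 4.3). At stake is whether the reported systemic rates describe what followed the vaccine or a mixture of that and what volunteers brought with them. The protocol does use a baseline elsewhere: laboratory safety is defined as change from baseline in Section 4.4, and Section 8.9.1 acts on grade changes from baseline. The subjective symptoms have no equivalent.

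**Working it through.** **Step 1: can a pre-existing symptom reach the count?**

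| Possible filter | Where | What it does |
|---|---|---|
| Deferral at vaccination | 6.4.4 | Addresses moderate or severe illness and raised temperature; mild symptoms pass |
| Day 0 evaluation and history | 5.3, Table 1 | Takes place, but no solicited-symptom grade is specified |
| Day 0 adverse event review | Table 1 | Scheduled after the dose |
| Diary timing | 7.5.2 | May show some onset times; no rule on onset before the dose |
| Adverse event definition | 8.1 | Covers events during or after administration; no pre-dose grade to apply it with |
| Causality assessment | 8.6 | Specified for unsolicited events |
| New-or-worsened rule | 4.4, 9.2 | Absent |

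No filter reliably stops a mild pre-existing symptom. Some may catch part of them.

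**Step 2: number of participants.** The Synopsis expects 50% of 40: 40 × 0.50 = 20, which reproduces its figure. One participant is 1/20 = 5 percentage points.

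**Step 3: possible size.** Let t be the true rate of a symptom caused by the vaccine and b the share of volunteers who have that symptom before the dose. The protocol gives no value for b; I assume 5-15%. If the two are independent and every pre-existing symptom is counted,

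observed rate = 1 − (1 − t)(1 − b), so the excess is b(1 − t).

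| True t | b = 5% | b = 10% | b = 15% |
|---|---|---|---|
| 10% | 1 − 0.90 × 0.95 = 14.5% | 1 − 0.90 × 0.90 = 19.0% | 1 − 0.90 × 0.85 = 23.5% |
| 20% | 1 − 0.80 × 0.95 = 24.0% | 1 − 0.80 × 0.90 = 28.0% | 1 − 0.80 × 0.85 = 32.0% |
| 30% | 1 − 0.70 × 0.95 = 33.5% | 1 − 0.70 × 0.90 = 37.0% | 1 − 0.70 × 0.85 = 40.5% |

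If only a fraction f of pre-existing symptoms is counted, the excess shrinks to f × b(1 − t); with f = 0 there is none.

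**Step 4: how often it would arise.** Among 20 participants the expected number with a given symptom beforehand is 20b: 1 at 5% and 2 at 10%. The chance of at least one is 1 − (1 − b)^20: 1 − 0.95^20 = 0.64 and 1 − 0.90^20 = 0.88.

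**Step 5: against sampling error.** The exact 95% interval planned in Section 9.1 runs from 5.7% to 43.7% for 4 of 20, a half-width of (43.7 − 5.7)/2 = 19 points. At t = 20% the excess for b = 5-10% is 4 to 8 points. This is small beside the sampling error, but it always runs in one direction and the interval does not reflect it.

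I give no figure for any systemic symptom taken together: these symptoms tend to occur in the same person, so multiplying across items as if independent would overstate the total.

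**The case against.** The strongest reply is the protocol's own definition. Section 8.1 defines an adverse event as something that may occur during or after administration, and solicited events are adverse events, so a headache present before the needle is arguably not one. Staff also evaluate the volunteer and take a history before the dose, the diary records timing, and Section 5.3 has a rule for "A volunteer who arrives at the clinic with fever". The case report form and diary card, which might hold a pre-dose symptom line, are not part of the protocol text. Whether to tabulate any occurrence or only new or worsened events is commonly settled in a statistical analysis plan. The outcome is secondary, the analysis is descriptive, no numerical threshold depends on these rates, and an overcount would overstate reactogenicity, not hide it.

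Much of this stands. It limits the point to subjective, mainly Grade 1 symptoms, and it means that the protocol has no explicit rule either way. It does not remove the point. The definition cannot be applied dependably to a symptom that continues or worsens when its earlier grade is not recorded, and a history does not necessarily yield that grade. A later analysis plan can choose the counting rule but cannot recreate a pre-dose measurement that was not taken.

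A reader might infer that pre-existing symptoms definitely are counted, that the rates are certainly inflated, or that nothing could be recovered afterwards. The documents support none of these: no section says such symptoms are to be counted, and history and diary timing may identify some of them.

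**Conclusion.** The point holds as a gap in data collection and endpoint definition, not as a demonstrated bias. A mild systemic symptom present on Day 0 can be counted as reactogenicity, the resulting error can only raise the rates, and it cannot be reliably corrected later without a pre-dose grade.

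Its size is unknown. The figures in the working rest on an assumed prevalence of 5-15%, on independence from true reactions and on every such symptom being counted, so they are upper readings for each prevalence. Rates of Grade 2 and above should be little affected, because moderate or severe illness is a ground for deferral. Fever is already checked before the dose. The primary immunogenicity outcomes are untouched. This is a worthwhile, inexpensive improvement to a secondary outcome.

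**What to change.** - **Table 1 and the Day 0 case report form:** add a pre-injection entry that grades each solicited systemic symptom on the Section 8.8 symptom scale. Temperature is already taken.
- **Sections 4.4 and 9.2:** report the number and percentage of participants with each symptom that is new, or of higher grade than the pre-injection record, within the existing window. Show the any-occurrence count beside it.

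The cost is one extra line on the form at a visit that already takes place, plus the wording changes. No visit or blood sample is added, and the rules on who is vaccinated and when do not change. One downside: a symptom present beforehand that the vaccine prolongs at the same grade would not count as new. The any-occurrence count beside it keeps such cases visible.
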